10. REPORTING CONVENTIONS

Means, medians, standard deviations, first quartile, third quartile and range values will be rounded to less decimal places than Stata output to the extent that informational integrity is unharmed. Proportions will be reported to two decimal places.

11. TECHNICAL DETAILS

Stata version 14 will be used for all data management, analysis, and figure creation. To produce tables, data will be exported into Word/Excel.

APPENDIX I: TABLE MOCK-UPS

Appendix I: Table Mock-Ups

**A Phase 1, Randomized Trial to Assess the Safety,
Reactogenicity, and Immunogenicity of a Combination HTNV
and PUUV DNA Vaccine Candidate Administered by
Electroporation**

Statistical Analysis Plan

**Version 2.0
April 16, 2018**

Table of Contents

TABLE 1.1: Ineligibility Summary of Screen Failures	1
TABLE 1.2: Analysis Population by Treatment Group.....	2
TABLE 1.3: Subject Disposition by Treatment Group.....	3
TABLE 1.4: Distribution of Protocol Deviations by Category, Type, and Treatment Group	4
TABLE 1.5: Summary of Demographic and Baseline Characteristics by Treatment Group	5
TABLE 1.6: Summary of Subjects with Pre-Existing Medical Conditions by MedDRA® System Organ Class and Treatment Group.....	6
TABLE 1.7: Visit Completion Rates by Treatment Group.....	7
TABLE 2.1: Injection Pain, Efficiency, and Speed by Treatment Group.....	8
TABLE 2.2: Global Summary of Adverse Events.....	10
TABLE 2.3.1: Number and Percentage of Subjects Experiencing Solicited Events by Symptom, Relationship to Study Product, and Treatment Group.....	11
TABLE 2.3.2: Number and Percentage of Subjects Experiencing Solicited Events by Symptom, Maximum Severity, and Treatment Group	12
TABLE 2.3.3: Number and Percentage of Subjects Experiencing Unexpected Adverse Events or Unexpected Suspected Adverse Reaction Considered Possibly, Probably, or Definitely Related by MedDRA® System Organ Class, Severity, and Treatment Group	14
TABLE 2.3.4: Number and Percentage of Subjects Experiencing Unexpected Adverse Events or Unexpected Suspected Adverse Reaction Considered Unrelated or Unlikely Related by MedDRA® System Organ Class, Severity, and Treatment Group	16
TABLE 3.1: Proportion of Seropositive Subjects at Each Blood Collection Time Point.....	17
TABLE 3.2: Proportion of Subjects that Ever Seroconverted at Each Blood Collection Time Point	18
TABLE 3.3: Duration of Seropositivity if Ever Seroconverted.....	19
TABLE 3.4: Geometric Mean Titers of the PsVNA50 at Each Blood Collection Time Point.....	20
TABLE 4.1: Safety Analysis Group Comparison: Ever Experienced Solicited Adverse Events	21
TABLE 4.2: Safety Analysis Group Comparison: Ever Experienced Unsolicited Adverse Events.....	22
TABLE 4.3: Immunogenicity Analysis: Ever Seroconverted.....	23

TABLE 1.1: Ineligibility Summary of Screen Failures

	Criterion	Frequency*
Inclusion	Any inclusion criterion [inclusion criterion 1] [inclusion criterion 2] [inclusion criterion 3]	
Exclusion	Any exclusion criterion [exclusion criterion 1] [exclusion criterion 2] [exclusion criterion 3]	
		Total:

*More than one criterion may be marked per subject

TABLE 1.2: Analysis Population by Treatment Group

Analysis Population	Reason Subjects Excluded	Group 1 (N=X)		Group 2 (N=X)		Group 3 (N=X)		Group 4 (N=X)		Group 5 (N=X)		Group 6 (N=X)		All Subjects (N=X)	
		n	%	n	%	n	%	n	%	n	%	n	%	n	%
Safety Population	Any Reason														
	[Reason 1, for example: Did not meet eligibility criteria]														
	[Reason 2]														
	[Reason 3]														
Immunogenicity Population	Any Reason														
	[Reason 1]														
	[Reason 2]														

*More than one criterion may be marked per subject

TABLE 1.3: Subject Disposition by Treatment Group

Subject Completed:	Group 1 (N=X)		Group 2 (N=X)		Group 3 (N=X)		Group 4 (N=X)		Group 5 (N=X)		Group 6 (N=X)		All Subjects (N=X)	
	n	%	n	%	n	%	n	%	n	%	n	%	n	%
Screened ^a	--	--	--	--	--	--	--	--	--	--	--	--	--	--
Enrolled/Randomized														
Immunization 1														
Immunization 2														
Immunization 3														
All Immunizations														
Visit 1 ^b														
Visit 2														
Visit 3														
Visit 4														
Visit 5														
Visit 6														
Visit 7														
Visit 8														
Visit 9														
Visit 10														
Visit 11														
Visit 12														

a) Subjects not assigned to groups at screening stage

b) Visit completion requires compliance for all scheduled tasks at each visit.

TABLE 1.4: Distribution of Protocol Deviations by Category, Type, and Treatment Group

Category	Deviation Type:	Group 1 (N=X)		Group 2 (N=X)		Group 3 (N=X)		Group 4 (N=X)		Group 5 (N=X)		Group 6 (N=X)		All Subjects (N=X)	
		# of Subj.	# of Dev.	# of Subj.	# of Dev.										
Treatment administration schedule	Any type														
	Out of window visit														
	Missed visit/visit not conducted														
	Missed treatment administration														
	Delayed treatment administration														
Follow-up visit schedule	Other														
	Any type														
	Out of window visit														
	Missed visit/visit not conducted														
	Other														
Protocol procedure/assessment	Any type														
	Incorrect version of ICF signed														
	Blood not collected														
	Urine not collected														
	Other specimen not collected														
	Too few aliquots obtained														
	Specimen result not obtained														
	Required procedure not conducted														
	Required procedure done incorrectly														
	Study product temperature excursion														
	Specimen temperature excursion														
	Other														
Treatment administration	Any type														
	Required procedure done incorrectly														
	Study product temperature excursion														
	Other														

TABLE 1.5: Summary of Demographic and Baseline Characteristics by Treatment Group

		Group 1 (N=X)	Group 2 (N=X)	Group 3 (N=X)	Group 4 (N=X)	Group 5 (N=X)	Group 6 (N=X)	All Subjects (N=X)
Sex – n(%)	Male	x (xx)	x (xx)					
	Female							
	Intersex							
Ethnicity – n(%)	Not Hispanic or Latino	x (xx)	x (xx)					
	Hispanic or Latino							
	Not Reported							
	Unknown							
Race – n(%)	American Indian or Alaska Native	x (xx)	x (xx)					
	Asian							
	Native Hawaiian or Other Pacific Islander							
	Black or African American							
	White							
	Multi-Racial							
	Unknown							
Age	Mean	x.x	x.x					
	Standard Deviation							
	1 st Quartile							
	Median							
	3 rd Quartile							
	Minimum							
	Maximum							

TABLE 1.6: Summary of Subjects with Pre-Existing Medical Conditions by MedDRA® System Organ Class and Treatment Group

MedDRA® System Organ Class	Group 1 (N=X)		Group 2 (N=X)		Group 3 (N=X)		Group 4 (N=X)		Group 5 (N=X)		Group 6 (N=X)		All Subjects (N=X)	
	n	%	n	%	n	%	n	%	n	%	n	%	n	%
Any SOC														
[SOC 1]														
[SOC 2]														
[SOC 3]														

Note: A subject is only counted once per SOC.

TABLE 1.7: Visit Completion Rates by Treatment Group

	Group 1 (N=X)	Group 2 (N=X)	Group 3 (N=X)	Group 4 (N=X)	Group 5 (N=X)	Group 6 (N=X)
# participants enrolled with scheduled visits						
# participants missing \geq 1 visit						
% participants missing \geq 1 visit						
# expected scheduled visits						
# total scheduled visits						
# missed visits						
% scheduled visits completed						

TABLE 2.1: Injection Pain, Efficiency, and Speed by Treatment Group

^aIf more than one syringe was used, data from the last syringe is included in this table.

Q1: first quartile; Q3: third quartile.

TABLE 2.2: Global Summary of Adverse Events

Number of Participants Immunized= N	Possibly, Probably or Definitely Related Adverse Events	
	All Adverse Events	Events
Subjects with at least one solicited AE by 16 days of immunization [n (%)]	x (xx)	x (xx)
Total # solicited AEs [n (maximum severity grade)]	x (Grade X)	x (Grade X)
Subjects with a solicited Grade 3 AE [n (%)]	x (xx)	x (xx)
Subjects with at least one solicited local AE	x (xx)	x (xx)
Total # local AEs	x (Grade X)	x (Grade X)
Average # local AEs/volunteers experiencing local AEs	x.xx	x.xx
Subjects with at least one solicited systemic AE	x (xx)	x (xx)
Total # systemic AEs	x (Grade X)	x (Grade X)
Average # systemic AEs/volunteers experiencing systemic AEs	x.xx	x.xx
Subjects with at least one unsolicited AE within 32 days of immunization [n (%)]	x (xx)	x (xx)
Total # unsolicited AEs within 32 days of immunization [n (maximum severity grade)]	x (Grade X)	x (Grade X)
Subjects with an unsolicited Grade 3 AE [n (%)]	x (xx)	x (xx)
Subjects experiencing an SAE ^a [n (%)]	x (xx)	x (xx)
Total # of SAEs [n (maximum severity grade)]	x (Grade X)	x (Grade X)

a) An adverse event or suspected adverse reaction is considered “serious” (SAE) if, in the view of either the investigator or sponsor, it results in any of the following outcomes:

- Death
- Life-threatening adverse event
- Inpatient hospitalization or prolongation of existing hospitalization
- Persistent or significant incapacity or substantial disruption of the ability to conduct normal life functions
- Congenital anomaly/birth defect

TABLE 2.3.1: Number and Percentage of Subjects Experiencing Solicited Events by Symptom, Relationship to Study Product, and Treatment Group

NOTE: Table will be repeated for each injection dose

Symptom	Relationship to Study Product	Group 1 (N=X)		Group 2 (N=X)		Group 3 (N=X)		Group 4 (N=X)		Group 5 (N=X)		Group 6 (N=X)	
		n	%	n	%	n	%	n	%	n	%	n	%
Any Symptom	Related												
	Unrelated												
Redness, swelling, bruising, or pain (to include tenderness) at the injection site	Related												
	Unrelated												
Fever	Related												
	Unrelated												
Myalgia	Related												
	Unrelated												
Headache	Related												
	Unrelated												
Lymphadenopathy	Related												
	Unrelated												
Axillary pain or discomfort	Related												
	Unrelated												
Tachypnea	Related												
	Unrelated												
Fatigue	Related												
	Unrelated												

TABLE 2.3.2: Number and Percentage of Subjects Experiencing Solicited Events by Symptom, Maximum Severity, and Treatment Group

NOTE: Table will be repeated for each injection dose

Symptom	Severity Grade	Group 1 (N=X)		Group 2 (N=X)		Group 3 (N=X)		Group 4 (N=X)		Group 5 (N=X)		Group 6 (N=X)	
		n	%	n	%	n	%	n	%	n	%	n	%
Any Symptom	None												
	1												
	2												
	3												
	Any												
Redness, swelling, bruising, or pain (to include tenderness) at the injection site	None												
	1												
	2												
	3												
	Any												
Fever	None												
	1												
	2												
	3												
	Any												
Myalgia	None												
	1												
	2												
	3												
	Any												

Symptom	Severity Grade	Group 1 (N=X)		Group 2 (N=X)		Group 3 (N=X)		Group 4 (N=X)		Group 5 (N=X)		Group 6 (N=X)	
		n	%	n	%	n	%	n	%	n	%	n	%
Headache	None												
	1												
	2												
	3												
	Any												
Lymphadenopathy	None												
	1												
	2												
	3												
	Any												
Axillary pain or discomfort	None												
	1												
	2												
	3												
	Any												
Tachypnea	None												
	1												
	2												
	3												
	Any												
Fatigue	None												
	1												
	2												
	3												
	Any												

TABLE 2.3.3: Number and Percentage of Subjects Experiencing Unexpected Adverse Events or Unexpected Suspected Adverse Reaction Considered Possibly, Probably, or Definitely Related by MedDRA® System Organ Class, Severity, and Treatment Group

Symptom	Severity Grade	Group 1 (N=X)		Group 2 (N=X)		Group 3 (N=X)		Group 4 (N=X)		Group 5 (N=X)		Group 6 (N=X)	
		n	%	n	%	n	%	n	%	n	%	n	%
Any													
[SOC 1]	1												
	2												
	3												
Any													
[SOC 2]	1												
	2												
	3												
Any													

TABLE 2.3.4: Number and Percentage of Subjects Experiencing Unexpected Adverse Events or Unexpected Suspected Adverse Reaction Considered Unrelated or Unlikely Related by MedDRA® System Organ Class, Severity, and Treatment Group

Table follows Table 2.3.3 formatting.

TABLE 3.1: Proportion of Seropositive Subjects at Each Blood Collection Time Point

Collection Point	Group 1 (N=X)		Group 2 (N=X)		Group 3 (N=X)		Group 4 (N=X)		Group 5 (N=X)		Group 6 (N=X)	
	n	%	n	%	n	%	n	%	n	%	n	%
1	x	xx										
	[x,x]		[x,x]		[x,x]		[x,x]		[x,x]		[x,x]	
2												
3												
4												
5												
6												
7												

Note: 95% confidence intervals for sample proportion in brackets

TABLE 3.2: Proportion of Subjects that Ever Seroconverted at Each Blood Collection Time Point

Collection Point	Group 1 (N=X)		Group 2 (N=X)		Group 3 (N=X)		Group 4 (N=X)		Group 5 (N=X)		Group 6 (N=X)	
	n	%	n	%	n	%	n	%	n	%	n	%
1	x	xx										
	[x,x]		[x,x]		[x,x]		[x,x]		[x,x]		[x,x]	
2												
3												
4												
5												
6												
7												

Note: 95% confidence intervals for sample proportion in brackets

TABLE 3.3: Duration of Seropositivity if Ever Seroconverted

	Group 1 (n=x)	Group 2 (n=x)	Group 3 (n=x)	Group 4 (n=x)	Group 5 (n=x)	Group 6 (n=x)
Mean						
Standard Deviation						
95% CI for Mean						
1st Quartile						
Median						
3rd Quartile						
Min						
Max						

TABLE 3.4: Geometric Mean Titers of the PsVNA50 at Each Blood Collection Time Point

Collection Point	Group 1 (N=X)		Group 2 (N=X)		Group 3 (N=X)		Group 4 (N=X)		Group 5 (N=X)		Group 6 (N=X)	
	μ	SD										
1	x	x	x	x	x	x	x	x	x	x	x	x
	[x,x]		[x,x]		[x,x]		[x,x]		[x,x]		[x,x]	
2												
3												
4												
5												
6												
7												

Note:

- μ = mean; SD = standard deviation
- 95% confidence intervals for sample proportion in brackets

TABLE 4.1: Safety Analysis Group Comparison: Ever Experienced Solicited Adverse Events

Group:	1	2	3	4	5	6	P-value ¹
N=	x	x	x	x	x	x	
% Reporting	xx	xx	xx	xx	xx	xx	
(95% CI)	(x,x)	(x,x)	(x,x)	(x,x)	(x,x)	(x,x)	
Pair 1	•	•					x
Pair 2		•	•				x
Pair 3				•	•		x
Pair 4	•				•		x
Pair 5		•			•		x
Pair 6		•				•	x
Pair 7			•		•		x

¹P-value obtained from a two-sided Fisher's exact test

TABLE 4.2: Safety Analysis Group Comparison: Ever Experienced Unsolicited Adverse Events

Group:	1	2	3	4	5	6	P-value ¹
N=	x	x	x	x	x	x	
% Reporting (95% CI)	xx (x,x)	xx (x,x)	xx (x,x)	xx (x,x)	xx (x,x)	xx (x,x)	x
Pair 1	•	•					x
Pair 2		•	•				x
Pair 3				•	•		x
Pair 4	•			•			x
Pair 5		•		•			x
Pair 6	•				•		x
Pair 7			•		•		x

¹P-value obtained from a two-sided Fisher's exact test

TABLE 4.3: Immunogenicity Analysis: Ever Seroconverted

Group:	1	2	3	4	5	6	P-value ¹
N=	x	x	x	x	x	x	
% Reporting	xx	xx	xx	xx	xx	xx	x
(95% CI)	(x,x)	(x,x)	(x,x)	(x,x)	(x,x)	(x,x)	
Pair 1	•	•					x
Pair 2			•	•			x
Pair 3					•	•	x
Pair 4	•				•		x
Pair 5			•		•		x
Pair 6		•				•	x
Pair 7				•		•	x

¹P-value obtained from a two-sided Fisher's exact test

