There has been at least one reported instance of an aborted TDS-IM V1.0 administration procedure with observations consistent with injection needle contact with the underlying bone. This was associated with acute pain at the penetration site and increased difficulty in the withdrawal of the device. Subsequent inspection of the Cartridge revealed deformation of the needle consistent with impact on the bone. The TDS-IM V1.0 device registered an error code and no vaccine was delivered. This was believed to be due to an inaccurate measurement of skinfold thickness. Following the incident, associated adverse events were limited to mild transient soreness at the penetration site. Although the specific cause of this event could not be definitively established based on the available information, inspection of the device was sufficient to rule out device malfunction (ie, the needle did not penetrate beyond the specified depth setting). To ensure intramuscular injection, proper selection of the injection site as well as assessment and setting of the injection depth are important factors in procedure administration. In particular, care should be taken in specific subjects or subject populations with low muscle mass (eg, sarcopenia) to ensure that an administration site with adequate muscle thickness (eg, vastus lateralis) is selected for injection. Specifically, any selected administration site should have sufficient muscle mass to accommodate the 1-inch/25-mm maximum penetration depth of the device. To mitigate the risk of this happening again, only the PI or qualified, designated personnel with PI oversight will take all skinfold measurements and study staff training on skinfold measurement and device usage will be performed and documented by Ichor for implementation of this study. This should decrease the possibility of inter-rater variability errors in measurement and avoid overestimations of soft tissue girth. The measurement may be repeated, as needed, throughout the study or if any study team member has a concern about the accuracy of the measurement (eg, if there seems to be a discrepancy between the volunteer's body habitus and the indicated depth setting for the TDS-IM V1.0 device).

There have been no occurrences of excessive energy delivery in any of the nonclinical and clinical studies conducted with the pulse stimulator to date.

TDS-ID Device:

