The study may enroll 6 randomized groups of 12 subjects each for a total of 82 subjects (This accounts for 10 replacement subjects for Group 6, impacted by COVID). The study had initially planned to enroll 6 randomized groups of 12 subjects each, for a total of 72 subjects. Ten subjects in Cohort 6 may be replaced because vaccination and data collection were negatively impacted in this group by COVID-19 pandemic quarantine restrictions. This approach will ensure at least 60 subjects complete all vaccinations at around 10 subjects per group, taking possible attrition into account. Subjects will receive one dose of vaccine on each of Days 0, 28, and 56 and will be followed until Day 220.

The HTNV and PUUV DNA vaccines will be administered to subjects as follows:

Group 1⁴: 0.6 mg HTNV by ID EP

⁴ Sentinel subjects will not be included for Groups 1 and 3 because the dose is lower than the 2.0 mg/mL dose that was previously evaluated for these products.

Group 2: 3.0 mg HTNV by IM EP

Group 3: 0.6 mg PUUV by ID EP

Group 4: 3.0 mg PUUV by IM EP

Group 5: 1.2 mg HTNV/PUUV by ID EP

Group 6: 6.0 mg HTNV/PUUV by IM EP

Every subject will receive 1 injection on Days 0, 28, and 56 for a total of 3 injections.

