6.3. Measures Taken to Minimize/Avoid Bias

6.3.1. Randomization

A randomization plan will be used to allocate subjects into experimental groups, per the study priorities described in Section 6.2. In addition, as of Version 5.0, ten replacement subjects will be enrolled into Group 6. A fixed random allocation will ensure that the groups are balanced in size at the end of experiment.

Designated study personnel (excluding the principal investigator [PI] and other investigators) will fill the vaccine cohorts as potential subjects successfully complete the screening process and are deemed eligible to participate by the PI (or another designated investigator). For the purposes of this study, the groups will be defined as follows, and each subject will receive one dose of vaccine on Days 0, 28, and 56.

Group 1 (12 subjects): HTNV by ID EP

Group 2 (12 subjects): HTNV by IM EP

Group 3 (12 subjects): PUUV by ID EP

Group 4 (12 subjects): PUUV by IM EP

Group 5 (12 subjects): HTNV/PUUV by ID EP

Group 6 (22 subjects): HTNV/PUUV by IM EP

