A complete listing of adverse events for each subject will provide details including severity, relationship to study product, onset, duration, and outcome. Laboratory results will be summarized by laboratory parameter, severity, study day, and study group. Figures 1.3 and 1.4 will present details of adverse effects, by group and visit number. Tables 2.1 to 2.3.4 present data about adverse effects.

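### SAP Table 2.1 takes only the last syringe when several were used, so pain and performance data from earlier syringes for that injection are left out of the table

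*SAP*

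**What the plan says.** The table shell is titled "TABLE 2.1: Injection Pain, Efficiency, and Speed by Treatment Group". Footnote a says that if "more than one syringe was used, data from the last syringe is included in this table". Neither document, in the text available, gives a reason for the rule, says when a second syringe would be used, or defines pain, efficiency and speed as this table uses them.

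Three other places bear on the rule:

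- SAP 8.5 places the table among the safety outputs: "Tables 2.1 to 2.3.4 present data about adverse effects".
- Protocol 6.2 plans one injection per vaccination day: "Every subject will receive 1 injection on Days 0, 28, and 56 for a total of 3 injections".
- Protocol 4.5.1.1 reports a failed IM application in earlier experience: "There has been at least one reported instance of an aborted TDS-IM V1.0 administration procedure". On pain it says "This was associated with acute pain at the penetration site and increased difficulty in the withdrawal of the device". On delivery it says "The TDS-IM V1.0 device registered an error code and no vaccine was delivered".

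**The concern.** The footnote is a stated rule for choosing data, and the choice may depend on the outcome. With one injection planned per visit, a second syringe is a departure from plan, and a failed or incomplete first attempt is a natural explanation. Keeping only the syringe that ended the sequence would then tend to keep the attempt that worked and drop the one that did not.

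The measures concerned bear on how tolerable the procedure is. The primary objective is safety and reactogenicity by IM or ID electroporation, and Protocol 4.5.1 and 4.5.1.3 say that product and device risks may have to be considered together. Judging by titles and visible shells, Table 2.1 is the only planned group table that isolates injection pain. At stake is whether a reader of that table sees the pain and performance of all syringes used for an injection, or only of the last.

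**Working it through.** The plan states no figure for this table, so there is nothing to reproduce. The check compares passages and then gives a sense of scale.

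**1. What the rule drops.** It applies only when an injection used more than one syringe. Data from all syringes but the last are then left out, for whichever measures carry marker a. An attempt that was abandoned and not repeated is itself the last syringe, so it stays in.

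**2. Whether another output supplies the missing summary.**

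| Output | What it carries | What it lacks |
|---|---|---|
| SAP Tables 2.3.1 and 2.3.2 (solicited events, repeated for each dose) | Injection-site pain, with no syringe rule; 2.3.2 uses maximum severity | Pain shares one row with redness, swelling, bruising and tenderness |
| SAP Listing 1.11.3 | Solicited events by subject | Same pooling |
| SAP Table 1.4 and Listing 1.2 (deviations) | Administration errors | No named category for repeat syringes or device failure |
| Protocol 6.4.4 (accountability) | Record of malfunctioning cartridges | No visible SAP table or listing reports it |
| SAP Listing 1.10 | Dose dates | No attempts or syringes |

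None of these is a visible per-group summary of injection pain, or of repeat syringes, over all attempts.

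**3. Scale, on assumed rates.** The documents give no rate r of injections needing more than one syringe; 1%, 5% and 10% are assumptions.

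- Injections per 12-subject group: 12 × 3 = 36.
- Injections in Group 6 ("Group 6 (22 subjects): HTNV/PUUV by IM EP"): 22 × 3 = 66. This is a ceiling, because the ten added places replace subjects whose vaccination was disrupted.
- Chance that a group has at least one affected injection, taking injections as independent: 1 − (1 − r)^n.

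| Assumed r | n = 36 | n = 66 |
|---|---|---|
| 1% | 0.304 | 0.485 |
| 5% | 0.842 | 0.966 |
| 10% | 0.977 | 0.999 |

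Suppose k of 36 injections had one failed syringe followed by a successful one. Counting all attempts, the failed share is k/(36 + k): 1/37 = 2.7%, 2/38 = 5.3%, 3/39 = 7.7%. A last-syringe summary gives 0% in each case.

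For pain, suppose the dropped syringe scored d points above the last one. The group mean of worst pain per injection then exceeds the last-syringe mean by d × k/36. With d = 3 that is 3 × 1/36 = 0.08 points for k = 1 and 3 × 3/36 = 0.25 points for k = 3. The pain scale is not visible, so d is also an assumption. If the last syringe hurt more than the first, worst pain equals last-syringe pain and nothing is lost.

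**The case against.** The strongest reply is that much of the case rests on what cannot be seen.

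- **The table body is not in the available text.** Marker a may attach to one measure only, and a row may already count syringes or failures. This stands, so the point covers only the measures marked a, and the count is requested only if absent.
- **Neither document says why a second syringe is used.** The aborted IM procedure is not said to have been repeated with a new syringe, and the protocol discusses device faults in terms of the cartridge. This stands. That a second syringe signals a problem is an inference from the single planned injection.
- **The measures are not listed endpoints, and the SAP calls all analyses exploratory.** Pain is also a solicited event, and Protocol 8.4 has the maximum reported intensity entered in the eCRF. This stands and lowers the priority. It does not supply a separate pain summary, because the solicited tables pool pain with other local signs.

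A reader might infer that the rule hides painful failed attempts from the safety analysis altogether. The documents do not support that: such events can still reach the solicited-event, deviation and cartridge records, and an unrepeated abort stays in Table 2.1.

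**Conclusion.** The point holds in a narrow sense. Footnote a leaves pain and performance data from earlier syringes out of Table 2.1 for the measures it covers, and no other visible group table isolates injection pain. The table could understate procedural pain and overstate performance. That direction depends on two unstated conditions: that a second syringe usually follows a failed attempt and that the last one usually succeeds. For pain, the dropped attempt must also have hurt more than the last.

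The size is unknown. The figures in the working rest on assumed rates. The report of at least one aborted IM procedure, among the more than 700 subjects dosed with that device (Protocol 4.4.2.4), does not establish a repeat rate for this trial.

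It is tempting to conclude that the IM and ID comparison is tilted toward the less reliable device. That would need failure rates that differ by device, and the documents give none for either, so no such distortion can be claimed. Priority: minor.

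**What to change.** Change footnote a and the Table 2.1 shell as follows:

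- Report pain as the worst value over all syringes used for that injection.
- Add, by group and dose number, the count of injections needing more than one syringe, if the shell does not already show it.
- Show efficiency and speed for the first syringe where recorded.
- Keep the last-syringe summary as a second panel if wanted, with one sentence giving its reason.

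A possible footnote: *Where several syringes were used for one injection, pain is the highest value recorded over all of them; efficiency and speed refer to the first syringe where recorded; the number of such injections is shown.*

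The cost is one more panel in a descriptive table. No new data collection is proposed. Choosing the last syringe suggests that data are held per syringe, but the eCRF is not visible. If only the last syringe was recorded, the footnote should say so and the count should be given where it can be recovered.

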10.6.1. Methods/Timing for Assessing, Recording, and Analyzing Safety Endpoints

AEs, solicited AEs, and SAEs will be assessed at all study visits, documented in the source records, and recorded on the eCRFs using accepted medical terms and/or the diagnoses that accurately characterize the event. When a diagnosis is known, the AE term recorded on the eCRF will be the diagnosis rather than a constellation of symptoms. The investigator will assess all AEs for seriousness, relationship to investigational product, severity, and other possible etiologies. When an adverse event has not resolved by study closure, it will be documented on the AE eCRF as "ongoing."

The time frame for the collection of AEs and SAEs begins at the first administration of investigational product through the end of the study.

The timeframe for the collection of solicited AEs begins at the first administration of investigational product through 14 days following each dose of investigational product (the first 14 days will be assisted with a memory aid).

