3.3. Primary Endpoints

The primary endpoints align with the safety objective. The nature, frequency, and severity of adverse events (AEs) and/or serious adverse events (SAEs) associated with TDS-EP-based administration of HTNV and PUUV DNA vaccines.

- The occurrence of solicited local and systemic AEs occurring from the time of each injection through 14 days following the procedure (memory aid to assist with the first 14 days)
- The occurrence of vaccine-related unsolicited AEs from the time of the first injection through 28 days following each injection
- The occurrence of SAEs from the time of the first injection through the final study visit for each subject (approximately 6 months post-last vaccination)
- The occurrence of clinical safety laboratory AEs through 14 days following each study vaccination.

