8.5.3. Solicited Events and Symptoms

A solicited AE is a predetermined event, identified in the Investigator's Brochure, which may reflect safety concerns related to the investigational product. The solicited AEs for this study include:

- Redness, swelling, bruising, pain or tenderness at the injection site
- Fever
- Myalgia (general muscle aches)
- Headache
- Lymphadenopathy
- Axillary pain or discomfort
- Tachypnea
- Fatigue

The study analysis will include Solicited AEs occurring from the time of each injection through 14 days following each procedure. Tables 2.3.1 and 2.3.2 will summarize Solicited AEs by the number and percentage of subjects experiencing solicited events by symptom, relationship to study product, treatment group, and maximum severity.

All reported solicited AEs will be provided in Listing 1.11.3.

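### Three row labels in SAP Table 2.2 count adverse events to 16 and 32 days after immunization, while the primary safety endpoints close at 14 and 28 days

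*SAP*

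**What the plan says.** SAP 3.3 defines two of the primary safety endpoints by time since injection. The solicited one is "The occurrence of solicited local and systemic AEs occurring from the time of each injection through 14 days following the procedure". The unsolicited one is "The occurrence of vaccine-related unsolicited AEs from the time of the first injection through 28 days following each injection". Protocol 6.1 and 10.2 give the same two windows.

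Two further sections bear on the solicited window only. SAP 8.5.3 says "The study analysis will include Solicited AEs occurring from the time of each injection through 14 days following each procedure". Protocol 10.6.1 says "The timeframe for the collection of solicited AEs begins at the first administration of investigational product through 14 days following each dose". The same Protocol section collects adverse events in general from the first dose to the end of the study, with no 28-day limit.

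The shell for Table 2.2 in SAP Appendix I, the global summary of adverse events, uses other limits in three of its 14 rows:

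- "Subjects with at least one solicited AE by 16 days of immunization"
- "Subjects with at least one unsolicited AE within 32 days of immunization"
- "Total # unsolicited AEs within 32 days of immunization"

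The remaining solicited rows and the unsolicited Grade 3 row carry no window.

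**The concern.** Safety is the primary objective, and Table 2.2 is the table that summarizes it. As the SAP stands, a programmer meets one window in the endpoint definition and another in the shell, with nothing to say which governs. If the shell is followed, the reported unsolicited counts describe an endpoint other than the planned one, and the solicited row is cut differently from the symptom-level tables that fall under SAP 8.5.3.

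The unsolicited side is the more exposed. Events after day 28 will be in the database, so a 32-day cut has data to pick up, and no other shell would show the 28-day count.

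**Working it through.** **1. The windows side by side**

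| Source | Solicited | Unsolicited |
|---|---|---|
| SAP 3.3; Protocol 6.1 and 10.2 | 14 days | 28 days |
| SAP 8.5.3 | 14 days | not addressed |
| Protocol 10.6.1 (collection) | 14 days | to end of study |
| Protocol 8.4 (memory aid) | 14 days | not applicable |
| SAP Table 2.2 | 16 days (one row) | 32 days (two rows) |

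**2. Where 16 and 32 may come from.** Protocol 8.1.3 and 8.1.4 allow ±2 days on the Day 14 visit and ±4 days on the Day 28, 56 and 84 visits. 14 + 2 = 16 and 28 + 4 = 32, so the table's figures are reproduced by adding the visit tolerance to the endpoint window. This is an inference. Neither document states the rule. A visit tolerance governs when a subject may be seen, whereas the endpoint is defined by when the event occurs.

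**3. Unsolicited days at risk.** Count the union of the post-dose windows, including the dose days.

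- Doses on Days 0, 28 and 56 with a 28-day window: Days 0 to 84, which is 85 days.
- The same doses with a 32-day window: Days 0 to 88, which is 89 days.
- Excess: 89 − 85 = 4 days (Days 85 to 88), and 4/85 = 4.7%.
- Doses moved within the permitted ±4 days: the largest excess found was with doses on Days 0, 24 and 60, where 82 days become 90. That is 8 extra days (Days 53 to 56 and 89 to 92), and 8/82 = 9.8%.

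**4. What 4 days could mean for a percentage.** The documents give no event rates by day. Assume, for illustration, a constant rate and a proportion p of subjects with at least one event over 85 days. Over 89 days the proportion is 1 − (1 − p)^(89/85).

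| Over 85 days | Over 89 days |
|---|---|
| 30% | 31.2% |
| 50% | 51.6% |
| 70% | 71.7% |

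**5. Solicited days.** Counting dose days, the label covers 3 × 17 = 51 days instead of 3 × 15 = 45. The added 6 days lie outside both the memory aid and the defined solicited collection period. Protocol 10.6.1 also has solicited events assessed at all visits, so an occasional onset on day 15 or 16 could be recorded, most readily when the visit falls late.

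**6. Other shells that might carry the endpoint.** Tables 2.3.1 and 2.3.2 report solicited events by group and dose under the 14-day rule of SAP 8.5.3, so that endpoint is still tabulated. Tables 2.3.3 and 2.3.4 cover unexpected events, which is a different category from unsolicited. Table 4.2 covers unsolicited events ever experienced, with no window. Table 2.2 is therefore the only shell with a windowed unsolicited count, and its window is 32 days.

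**The case against.** The strongest reply is that this is a labelling slip with little numerical effect. Only three of 14 rows are affected, the table has no treatment-group columns and no test, and SAP section 5 calls all analyses exploratory. Appendix I is headed Version 2.0, April 16, 2018, inside an SAP headed Version 4.0, January 25, 2019, so the shell may simply be out of date. All of that stands, and it limits the size of the point. It does not remove it, because the unsolicited endpoint has no other windowed shell.

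A reader might also infer more than the documents support:

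- **That every cited section fixes both windows.** SAP 8.5.3 and Protocol 10.6.1 support the 14-day limit only. The 28-day limit rests on SAP 3.3 and Protocol 6.1 and 10.2.
- **That solicited follow-up grows by about 13% (45 to 51 days).** That counts days on a label. With solicited collection closed at day 14, few or no solicited events would be added.
- **That one event would be solicited in one table and unsolicited in another.** The documents define a solicited event by type and give it a separate window. They do not say that a listed symptom starting on day 15 becomes unsolicited, and no pair of shells is shown in which the switch would occur.
- **That a 32-day window attributes events to the wrong dose.** Table 2.2 is not split by dose. Overlap with the next dose can also arise with 28 days, since dose 2 is allowed from Day 24.

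**Conclusion.** The mismatch is real and lies within the SAP as well as between the SAP and the Protocol. Followed as written, the two 32-day rows would include events outside the planned 28-day endpoint: 4 extra days at nominal dosing (+4.7% of days at risk), and up to 8 days (+9.8%) within the dosing tolerance. Under a constant event rate that moves a subject percentage by one to two points. The true shift depends on onset rates on the added days, which the documents do not give.

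For solicited events the likely consequence is a possible disagreement with Tables 2.3.1 and 2.3.2, with little change in the count. The point is modest in size. It should still be settled before database lock, because it concerns how a primary endpoint is counted and costs almost nothing to correct.

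**What to change.** In Table 2.2, change the 16-day label to 14 days after each injection, and both 32-day labels to 28 days after each injection. Apply the cut by event onset date, not visit date. Apply the same windows to the eight solicited rows that have no label and to the unsolicited Grade 3 row, so that the whole table rests on one definition.

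If the sponsor did intend a visit-window allowance, it would have to be stated, justified and carried into the endpoint definitions and every adverse event table, which is a larger change.

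The cost is a few row labels and a date cut in the table program. Counts may be slightly lower, because unsolicited onsets beyond 28 days after the most recent dose drop out of those rows. They remain in the database.
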